The primary hypothesis is that there is a better anesthetic stability in the deep NMB group (Group 2) and that this is translated as a reduction of the BIS signal variability and a reduction in the required effect-site concentrations of propofol and remifentanyl (representative of the total drug consumption).

b) Secondary objectives

As a secondary objective, we will study the quality of recovery using the PQRS scale to see if maintaining a deep NMB level during surgery has an impact on the patients' quality of recovery.

The secondary hypothesis is that the quality of recovery (PQRS test) is better in the patients of Group 2.

Can adequacy of anesthesia depth and quality of recovery be influenced by the level of neuromuscular blockade?

6. Study design

Patients subjected to anterior cervical spine surgery under general intravenous anesthesia will be randomized to receive one of two protocols regarding the neuromuscular blockade:

- Group 1 – Standard Clinical Practice Group - standard NMB, with a standard rocuronium dose for intubation (0.6 mg/kg). If required, the reversal of neuromuscular block is performed with neostigmine.
- Group 2 – Deep NMB group - with a standard rocuronium dose for intubation (0.6 mg/kg), followed by a constant infusion of rocuronium (10-15 µg/kg/min) to guarantee a PTC less or equal to 2 on the TOF monitor (PTC is evaluated every 5 minutes). The reversal of neuromuscular block is performed with Sugammadex (4 mg/kg).

a) Primary Endpoints

- BIS signal variability using the measured standard deviation during the maintenance phase of anesthesia
- Required effect-site concentrations of remifentanyl and propofol

b) Secondary Endpoints

- PQRS results at 15 and 40 minutes after surgery (taking into account the patient baseline values of the PQRS test done on the pre-anesthetic visit)
- PQRS results at day 3 after surgery

c) Study type

This is an interventional, phase 4, double-arm, parallel, randomized, open-label, single-center study aiming to compare two anesthesia protocols.

Can adequacy of anesthesia depth and quality of recovery be influenced by the level of neuromuscular blockade?

d) Study Timeline

- Study Start Date: April 2016
- Study End Date: April 2017
- First Patient In: April 2016
- Last Patient In: April 2017
- Last Patient Out: April 2017
- Study Analysis: May 2017
- Publication: November 2017

Can adequacy of anesthesia depth and quality of recovery be influenced by the level of neuromuscular blockade?

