Data collection software (Rugloop® Software and TOF Link) are installed on a Laptop computer connected to the Base Primea infusion pumps, the BIS monitor, GE monitor and TOF Watch monitor, allowing for all data to be recorded online. The patient data files generated by the Rugloop® software will be accessed using the Labgrab® software and exported to excel files. TOF watch data will also be exported to excel files. All online data is posteriorly recorded in a patient individual CD. All non-electronic data will be noted on the patients' paper CRF and on the RugLoop® software notes toolbar.

The total doses of ephedrine and labetalol are used as a surrogate variable, since they are the drugs used in the response protocol to hemodynamic instability (MAP being outside the desired target range).

The following recorded data will be analyzed per patient and compared between the two study groups:

- BIS signal variability using the measured Standard deviation during the maintenance phase of anesthesia
- BIS average value during the maintenance phase of anesthesia
- Duration of periods of BIS values above 60 and below 40
- Average effect-site concentrations of propofol and remifentanil required during the maintenance of anesthesia
- Total doses of remifentanil, propofol, ephedrine and labetalol

Can adequacy of anesthesia depth and quality of recovery be influenced by the level of neuromuscular blockade?

- PQRS results at 15 and 40 minutes after surgery (taking into account the patient baseline values of the PQRS test done on the pre-anesthetic visit)
- Patient satisfaction evaluated using the specific PQRS questions

Can adequacy of anesthesia depth and quality of recovery be influenced by the level of neuromuscular blockade?

10. Safety evaluation

Each patient is considered to have ended participation in the study when he/she has completed the last telephone contact at 3 days post-surgery to verify the occurrence of any adverse events (AE) according to the pharmacovigilance guidelines, or prematurely discontinues from the trial.

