Sample size calculation with a power of 0.80 and an α of 0.05, considering the primary hypothesis of a reduction in the BIS variability (measured as the standard deviation) and a reduction in the propofol and remifentanil drug consumption (measured as the average effect-site concentration required) during maintenance of anesthesia.

To estimate the standard deviation of our population, we searched our database for standard clinical practice cases with: online data recording; cervical spine surgery; BIS average values within the recommended target values [40-60]; TCI anesthesia with propofol and remifentanil.

A total of 12 patients data were analyzed (mainly due to the lack of online recording during the procedures), the average BIS standard deviation was 8.7 ± 3.14 , and the average propofol and remifentanil effect-site concentrations were 2.68 ± 0.9 $\mu\text{g/ml}$ and 2.83 ± 0.8 ng/ml , respectively.

Can adequacy of anesthesia depth and quality of recovery be influenced by the level of neuromuscular blockade?

A 25% reduction on the BIS variability (standard deviation) was considered clinically relevant, and gave a minimum sample size of 26 per group.

A reduction on propofol average effect-site concentration of 20% was considered clinically relevant, and gave a minimum sample size of 34 per group.

A reduction on remifentanil average effect-site concentration of 20% was considered clinically relevant, and gave a minimum sample size of 24 per group.

Considering the above results and the possibility of patient exclusion due to external complications during surgery, a total of 35 patients per group will be included in the study.

The secondary variable, result of the PQRS test was not used in the sample size calculation, since there are no studies on the comparison of recovery after two different interventions and the data regarding sample calculation that the authors of PQRS showed us are for the recovery at 3 days post-surgery, which is not comparable to our study. Therefore we did not consider adequate to estimate a percentage difference for which we do not know the clinical reality.

The surrogate variables, consumption of ephedrine and labetalol will be analyzed since these drugs are used in the response protocol to target deviations, but they are not considered for the sample size calculation.

c) Level of statistical significance

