The sample was calculated at a significance level of 95%. A p-value below 0.05 is considered statistically significant.

d) Study termination

Data analysis is planned for the end of the trial. No early study termination is planned.

Can adequacy of anesthesia depth and quality of recovery be influenced by the level of neuromuscular blockade?

e) Missing data

Participants with missing primary endpoint data will not be included in the analysis.

f) Deviations

Any change to the statistical plan will be submitted to the competent authorities prior to its implementation.

g) Inclusion in analysis

All data will be included for the analysis (Intention to treat).

Can adequacy of anesthesia depth and quality of recovery be influenced by the level of neuromuscular blockade?

12. Direct access to source documents

The investigator will grant direct access to paper and/or electronic documentation pertaining to the clinical study (e.g. CRFs, source documents such as hospital patient charts and investigator study files) to authorized individuals, as the clinical trial monitors, auditors or health authority inspections. The objective of these accesses is to ensure the trial is being conducted according to local laws and regulations and ICH-GCP.

All site facilities related to the study conduct can be visited during an audit (e.g. pharmacy, laboratory, archives).

The investigator agrees to co-operate and provide assistance at reasonable times and places with respect to any monitoring or auditing activity.

Can adequacy of anesthesia depth and quality of recovery be influenced by the level of neuromuscular blockade?

13. Quality control and quality assurance

The study will be conducted in accordance with the current approved protocol, ICH GCP, relevant regulations and standard operating procedures.

Regular monitoring will be performed according to ICH GCP. Data will be evaluated for compliance with the protocol and accuracy in relation to source documents. Following written standard operating procedures, the monitors will verify that the clinical trial is conducted and data are generated, documented and reported in compliance with the protocol, GCP and the applicable regulatory requirements.

Inspections and Audits

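### Section 11e drops whole patients, not endpoints, when primary data are missing; this does not fit 11g and can discard valid data

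*Combined protocol and SAP*

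**What the plan says.** Two short rules in section 11 decide who is analysed. Under e) Missing data: "Participants with missing primary endpoint data will not be included in the analysis". Under g) Inclusion in analysis: "All data will be included for the analysis (Intention to treat". The plan defines no analysis sets, no evaluability rule for each endpoint and no sensitivity analysis for missing data.

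Section 6a lists as primary the BIS standard deviation during maintenance and "Required effect-site concentrations of remifentanyl and propofol", which makes three variables. The synopsis names BIS variability alone. PQRS is secondary.

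The primary data come from separate devices. Section 9b describes one laptop "connected to the Base Primea infusion pumps, the BIS monitor, GE monitor and TOF Watch monitor". PQRS is recorded on CRF forms (section 8, Assessment 3). Section 9b introduces its list of variables with "The following recorded data will be analyzed per patient and compared between the two study groups", and it also states: "The total doses of ephedrine and labetalol are used as a surrogate variable".

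On numbers, section 11b reports that a 20% reduction in propofol concentration "gave a minimum sample size of 34 per group", and that "a total of 35 patients per group will be included in the study".

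**The concern.** For a randomised patient who lacks a primary value, 11e taken literally says leave the patient out and 11g says keep the data. The plan does not say which governs.

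The unit of exclusion matters more than the clash of wording. A lost BIS trace says nothing about whether the pump log, the PQRS forms or the drug totals are valid. A rule that removes the participant discards all of them, including the satisfaction evaluation that section 8 schedules even at the Discontinuation Visit. At stake are some avoidable loss of data, a propofol comparison with little room for loss on the plan's own figures, and a choice of analysis population that could be made after the results are visible.

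**Working it through.** **1. The plan's own margin.** Section 11b gives propofol 2.68 with SD 0.9, so a 20% reduction is 0.536. With n = 2(z_α + z_β)²·SD²/Δ² at power 0.80:

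- one-sided α 0.05: 2(1.645 + 0.842)² × 0.81/0.2873 = 34.9, that is 35 (the plan states 34);
- two-sided α 0.05: 44.3, that is 45.

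The stated 34 therefore fits a one-sided calculation, although the plan does not state sidedness. On that basis 35 per group leaves one spare patient, and a second loss in a group goes below the stated minimum. On a two-sided basis there is no spare patient: t-test power at 35 per group with no loss is already 69%.

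**2. Patients leaving the propofol comparison.** The documents give no loss rate, so p, the loss per source (BIS monitor, pumps), is assumed to be 1, 2 or 5%.

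- Exclusion by endpoint: a patient leaves with probability p.
- Exclusion by patient, independent losses: q = 1 − (1 − p)² = 0.0199, 0.0396, 0.0975.
- Exclusion by patient, half of each source's losses shared: with s = p/2 and r = (p − s)/(1 − s), q = s + (1 − s)[1 − (1 − r)²] = 0.0150, 0.0299, 0.0744.
- Exclusion by patient, all losses shared: q = p.

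With X ~ Bin(35, q), P(X ≥ 2) = 1 − P(0) − P(1). For p = 2% and independent losses this is 1 − 0.243 − 0.351 = 0.406. By endpoint it is 1 − 0.493 − 0.352 = 0.155.

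| Rule and dependence | p = 1% | p = 2% | p = 5% |
|---|---|---|---|
| By patient, independent | 0.154 | 0.406 | 0.868 |
| By patient, half shared | 0.097 | 0.282 | 0.745 |
| By patient, all shared | 0.048 | 0.155 | 0.528 |
| By endpoint | 0.048 | 0.155 | 0.528 |

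These figures do not depend on which list of primary endpoints is used. If BIS variability is the only primary variable, a patient still leaves the propofol comparison when the BIS trace is lost (through 11e) or when the pump data are lost (nothing to analyse).

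**3. Power.** Two-sided t test, difference 0.536, SD 0.9, averaged over binomial losses in both groups:

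| | p = 1% | p = 2% | p = 5% |
|---|---|---|---|
| By patient, independent | 0.681 | 0.672 | 0.643 |
| By endpoint | 0.686 | 0.681 | 0.667 |
| Cost, percentage points | 0.5 | 0.9 | 2.4 |

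With all losses shared the cost is zero.

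**4. Secondary data.** Suppose PQRS is otherwise complete. Read literally, 11e removes on average 35q patients per group from it: 0.7, 1.4 or 3.4 with independent losses, and 35p = 0.35, 0.7 or 1.75 with all losses shared. Exclusion by endpoint removes none. This loss does not vanish when the recordings fail together.

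**The case against.** **A coherent reading exists.** 11g can mean that patients are analysed as randomised, and 11e that the primary analysis uses complete cases. The variable list in section 9b, the satisfaction evaluation at the Discontinuation Visit and the separate papers planned in section 17 for the primary and secondary objectives all lean that way. This stands, so a flat contradiction would be too strong a claim. But the plan does not state this reading, and even then 11e removes patients and not endpoints.

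**Losses may be shared.** One laptop records every device. The only recording failure the documents mention is the absence of online recording in routine cases, which left 12 patients for the sample size estimate (section 11b). That points towards losing the whole recording. This also stands: the independent-loss rows are the least favourable case, and with fully shared loss 11e costs the primary comparisons nothing extra. The loss of secondary data remains.

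**Only BIS variability may be primary.** On the synopsis version, pump loss triggers no exclusion and there is no other primary endpoint to lose. A lost BIS trace would still remove drug-concentration and PQRS data.

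**A reader might infer bias.** The trial is open label, and patients can be stopped for unresponsive MAP or on the investigator's judgement, so exclusions could look informative and arm-dependent. The documents do not support that conclusion. Section 9b has recorded data analysed per patient, which suggests that a stopped patient's recording is used. Apart from the neuromuscular block, induction and maintenance follow the same protocol in both groups, so similar losses would largely cancel. Neither a loss rate nor a direction is given.

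**Conclusion.** The point holds as an unreconciled rule that can cause a small, avoidable loss of data. The wording alone establishes that 11e is not limited to the affected endpoint and that nothing aligns it with 11g. The size rests on assumed loss rates and on assumed dependence between sources: at most about 0.5 to 2.4 points of propofol power at 1 to 5% loss per source, falling to nothing if losses are fully shared. The one-patient propofol margin comes from the plan's own figures and fits a one-sided calculation, whereas the power figures here are two-sided, so the two should not be combined. No bias is shown. The point should be settled before analysis, and it does not threaten the trial's validity.

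**What to change.** Replace 11e and align 11g with wording such as:

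> All randomised patients are analysed in their assigned group. A patient is left out of an endpoint only if that endpoint has no recorded data, and stays in all other analyses. For patients stopped early, all maintenance data recorded up to the stop are used. Stops and exclusions are reported by group and reason.

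Optionally, add a worst-case bound restricted to patients with no evaluable value: the highest observed value if in Group 2, the lowest if in Group 1. It is harsh. In 20,000 simulated trials at the planned effect, reassigning one patient per group cut the mean propofol difference from 0.536 to 0.395, or 74% of its size. It should be reported as a bound, not as a test to pass.

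The costs are a change of wording, a little more analysis, numbers of patients that differ across endpoints, and submission under 11f. Using recordings up to the stop also admits short BIS records, whose standard deviation tends to be low. Under an assumed AR(1) signal with a 5-minute constant, the mean sample SD is 0.626 of the true value at 10 minutes and 0.935 at 90. One 10-minute record then lowers the arm mean by (1 − 0.626/0.935) × 8.7/35 = 0.082, or 3.8% of the 2.175 target. With a 1-minute constant it is 1.1%. Reporting stops by group lets the reader judge this.
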